Effects of agonists of glucagon like peptide - 1 receptors (GLP-1R) on arterial stiffness, endothelial glycocalyx and coronary flow reserve in patients with coronary artery disease and patients with diabetes mellitus

ClinicalTrials.gov Identifier: NCT03010683

Document date: December 22, 2016

Study Protocol

Objectives

Arterial stiffness is associated with increased risk for cardiovascular disease. Moreover, the integrity of endothelial glycocalyx plays a vital role in vascular permeability, inflammation and elasticity. Agonists of glucagon like peptide - 1 receptors (GLP-1R) used in the treatment of type 2 diabetes mellitus (T2DM). This category includes exenatide and liraglutide. These drugs lower glucose levels by inhibiting the secretion of glucagon, promoting the release of insulin in response to hyperglycemia, slowing gastric emptying, and augmenting satiety. Clinical studies have shown that GLP-1R agonists have beneficial effects on cardiovascular function in both diabetic patients and healthy subjects. The purpose of this study is to investigate in patients with T2DM without coronary artery disease (CAD), patients with T2DM and CAD and obese patients with abnormal oral glucose tolerance test (OGTT), changes in arterial stiffness,

endothelial glycocalyx thickness and coronary reserve flow (CFR) after treatment with metformin or agonist GLP-1R.

Design

The investigators will study three groups matched for age and sex: 30 patients with type 2 diabetes mellitus (T2DM) without coronary artery disease (CAD), 30 patients with T2DM and CAD and 30 obese patients (BMI >30 Kg/m²) with abnormal oral glucose tolerance test (OGTT). It will be a randomized study with metformin or GLP-1R agonist treatment for 1 year. All subjects will receive for 1 year: (a) GLP-1R agonist or (b) metformin. At 0, 3, 6 and 12 months, where 0 is the starting point of treatment, blood samples will be collected.

Methods

At 0, 3, 6 and 12 months the investigators will measure:

- a. Carotid-femoral pulse wave velocity (PWV, m/sec) using tonometry by Complior (SP ALAM) and augmentation index (AI, %) by the method of arteriography (Arteriograph, TensioMed)
- b. Perfused boundary region (PBR, micrometers) of the sublingual arterial microvessels (ranged from 5-25 micrometers) using Sideview Darkfield imaging (Microscan, Glycocheck). Increased PBR is considered an accurate noninvasive index of reduced endothelial glucocalyx thickness.

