- c. Coronary flow reserve (CFR) in the left anterior descending artery after infusion of adenosine using Doppler echocardiography.
- d. Determination of the following parameters in blood: glucose, insulin, free fatty acids, triglycerides, glycerol, C reactive protein (CRP), transforming

growth factor-b (TGF-b), Lipoprotein-Associated Phospholipase A2 (LP-LPA2), tumor necrosis factor-a (TNF-a), interleukins 6 and 10 (IL6 and IL10), propeptide of type I procollagen (PIP), propeptide of procollagen type III (PIIINP), matrix metalloproteinases 9 and 2 (MMP), macrophage-colony stimulating factor (M-CSF), growth differentiation factor-15 (GDF-15), N-terminal pro b-type natriuretic peptide (NT-proBNP) and galectin-3.

Statistical analysis

All comparisons will be performed with the Statistical Package for Social Sciences 21.0 for Windows (SPSS Inc., Chicago, Illinois, USA). Categorical data will be compared between patients by contingency tables. Continuous variables will be tested for normality using the Kolmogorov-Smirnov test. Normally distributed variables will be given as mean \pm standard deviation. Data with a non-gaussian distribution will be expressed as median (interquartile range) and will be analyzed after transformation into ranks. Differences in mean values for each of the measured variables will be compared by t-test or paired t-test for continuous variables. For non-normally distributed data Mann Whitney or Wilcoxon signed-rank test will be used. The investigators will use parametric (Pearson r) and non-parametric (Spearman ρ) correlation coefficients to examine cross-sectional associations. ANOVA (general linear model, SPSS 22, SPSS Inc, Chicago, Ill) for repeated measurements will be applied a) for measurements of the examined markers at baseline, 3, 6 and 12 months after treatment used as a within-subject factor b) for the effects of treatment (liraglutide vs metformin), as a between-subject factors. The F and P

values of the interaction between time of measurement of the examined markers and type of treatment will be calculated. The F and P values of the comparison between treatments will be calculated. The Greenhouse-Geisser correction will be used when the sphericity assumption, as assessed by Mauchly's test, will not be met. Post hoc comparisons will be performed with Bonferroni correction.

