Comparisons between baseline or post-treatment values of measured markers between the 2 treatment groups will be performed using factorial ANOVA. Post hoc comparisons will be performed with Bonferroni correction. Statistical significance will be considered as $p < 0.05$. Baseline variables that will be statistically different ($p < 0.05$) among the 2 study groups or will be of clinical significance (HbA1c, weight, BMI and waist circumference) will be included in multivariate models as covariates.

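### The planned treatment F averages in the pre-treatment month 0, and no analysis fixes the marker's own baseline as a covariate

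*Combined protocol and SAP*

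**What the plan says.** All points are in the Combined protocol and SAP.

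- **Timing (Design).** "At 0, 3, 6 and 12 months, where 0 is the starting point of treatment, blood samples will be collected". Methods gives the same months for PWV, AI, PBR and CFR.
- **Repeated-measures model (Statistical analysis).** ANOVA is applied "for measurements of the examined markers at baseline, 3, 6 and 12 months after treatment used as a within-subject factor", and "for the effects of treatment (liraglutide vs metformin), as a between-subject factors".
- **Two F tests from that model.** For the first, F and P "values of the interaction between time of measurement of the examined markers and type of treatment will be calculated". For the second, "The F and P values of the comparison between treatments will be calculated".
- **A separate comparison at single times.** "Comparisons between baseline or post-treatment values of measured markers between the 2 treatment groups will be performed using factorial ANOVA". That sentence names no covariate.
- **Covariates.** Two routes are given. One is by test: "Baseline variables that will be statistically different" (p<0.05) between the arms. The other is by judgement: variables that "will be of clinical significance (HbA1c, weight, BMI and waist circumference) will be included in multivariate models as covariates". PWV, AI, PBR, CFR and the blood markers are not in the bracketed list.

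The plan does not say which of these tests is the principal treatment test. It gives no SD, effect size, visit correlation or power.

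**The concern.** The trial asks about changes after treatment. In a repeated-measures ANOVA the between-subject treatment F compares the arms on each patient's mean over all levels of the time factor. One of the four levels here precedes treatment. It adds nothing to the effect, and it adds whatever chance baseline difference exists between the arms.

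The comparison of post-treatment values has a related weakness. The best available predictor of a marker's later value is usually its own baseline, which is measured on everyone. The plan leaves its use to a baseline significance test, which randomisation makes positive about one time in twenty.

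At stake are precision and interpretation, not validity under the null. A non-significant treatment F could be read as no benefit when its estimate has been shrunk by construction.

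**Working it through.** **Inputs from the document.** Four time levels, with treatment starting at month 0; three groups of 30, so 90 patients; significance at 0.05.

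**Assumptions not in the document.** 1:1 allocation (45 per arm), two-sided test, SD 1 at each visit, compound symmetry with correlation ρ = 0.3, 0.5 or 0.7, no dropout. No other covariates are included. The plan states no power figure, so there is none to reproduce.

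**1. Dilution.** Let e3, e6 and e12 be the effects at months 3, 6 and 12, and m their mean. The four-visit F estimates

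(0 + e3 + e6 + e12)/4 = 3m/4.

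This needs no assumption about SD or correlation. For a constant 0.5 SD effect the target is 0.375 SD; simulation gave 0.373 to 0.376. The 3/4 is relative to m only:
- Effect rising in equal steps per visit to 0.5: (0 + 0.167 + 0.333 + 0.5)/4 = 0.25, half the 12-month effect.
- Effect linear in months: (0 + 0.125 + 0.25 + 0.5)/4 = 0.22.
- Waning effect 0.5/0.4/0.25: 1.15/4 = 0.2875, which exceeds the 12-month effect of 0.25 but is still 3/4 of m = 0.383.

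**2. Efficiency.**
- Four-visit mean: effect 3m/4, variance (1+3ρ)/4.
- Mean of months 3, 6 and 12 adjusted for own baseline: effect m, residual variance (1+2ρ)/3 − ρ² = (1−ρ)(1+3ρ)/3.
- Ratio of squared effect to variance, second over first: [3/((1−ρ)(1+3ρ))] ÷ [(9/16)·4/(1+3ρ)] = 4/[3(1−ρ)].

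This gives 1.90, 2.67 and 4.44 at ρ = 0.3, 0.5 and 0.7, whatever the shape of the effect.

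**3. Power.** Noncentral t for the single contrasts. For the interaction, noncentral F on 3 and 264 df with noncentrality (45/2)·Σ(e−ē)²/(1−ρ), summed over the four visits. Month 12 has variance 1 unadjusted and 1−ρ² adjusted. Entries are % at ρ = 0.3/0.5/0.7.

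| Effect (months 3, 6, 12) | Four-visit F | Interaction F | Month 12, unadjusted | Month 12, adjusted | Post-baseline mean, adjusted |
|---|---|---|---|---|---|
| Constant 0.5 | 72/61/52 | 51/67/89 | 65 | 69/77/91 | 94/95/99 |
| Equal steps to 0.5 | 40/32/27 | 39/53/77 | 65 | 69/77/91 | 65/68/80 |
| Linear in months to 0.5 | 32/26/21 | 39/52/77 | 65 | 69/77/91 | 54/56/69 |
| Waning 0.5/0.4/0.25 | 50/40/34 | 40/54/78 | 22 | 23/27/38 | 77/80/90 |

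**4. The conditional covariate rule.** The largest baseline difference that stays non-significant is t(0.975)·√(2/n): about 0.42 SD for 45 vs 45, and 0.75 SD for 15 vs 15 within one population. In simulation (constant effect, month 12) the rule selected the marker's baseline in 5.1 to 5.3% of trials. Power was 66/66/65%, against 70/77/90% with the baseline always in the model, so the rule recovers almost nothing.

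**5. Type I error.** Under the null, simulated rejection rates were 0.046 to 0.051 for the four-visit F, 0.049 to 0.051 for the interaction and 0.048 to 0.052 for the adjusted contrasts. None is inflated.

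**The case against.** **The interaction F is already planned and tests differential change.** This is correct, and month 0 does not dilute it. With a constant effect it beats the four-visit F at ρ = 0.5 and 0.7. But it spreads over 3 df, gives no single effect estimate and is not named as principal. Bonferroni post hoc comparisons could supply visit-level differences, but no one contrast is chosen. The interaction beats the baseline-adjusted mean in one of the twelve cells above (linear in months, ρ = 0.7: 77% vs 69%).

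**The power gaps ignore the planned covariates and the three populations.** This is the strongest point, and it stands as a limit on size. Suppose these explain a share q of the variance, all of it between patients (q is not in the document). The efficiency ratio becomes (1−q)·4/[3(1−ρ)]: 1.5/2.1/3.6 at q = 20% and 1.3/1.9/3.1 at q = 30%. At q = 30% and ρ = 0.5, power for a constant effect rises from 60% to 87% for the four-visit F, and month 12 is 80% without own baseline and 83% with it. A gain remains for the adjusted mean. The table is therefore the no-covariate case. The sentence specifying the repeated-measures model names no covariates, and the multivariate models that would carry them are not defined.

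**Rank-transformed markers escape the 3/4 rule.** The identity holds on whatever scale is analysed when the arms share a distribution at month 0; a simulation on pooled ranks gave a ratio of 0.748.

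**Adding own baseline to the four-visit model restores its F.** This is true: the adjusted effect and its residuals both scale by 3/4, so the test equals that of the adjusted post-baseline mean. It supports the fix, although the estimate would still need rescaling.

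**The list of clinically significant covariates may be illustrative.** If so, own baseline could be added by judgement. It is still not prespecified.

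**Conclusion.** The concern holds on both counts. The 3/4 dilution is algebra and needs no assumed SD or correlation. No reading of the covariate rule prespecifies the marker's own baseline.

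The size depends on assumptions. Under those stated, the baseline-adjusted post-baseline mean is 1.9 to 4.4 times as efficient as the four-visit F, or 1.3 to 3.1 times if other covariates explain 30% of the variance. Adjusted month 12 is not uniformly better. It trails the four-visit F with a constant effect at ρ = 0.3 (69% vs 72%) and with a waning effect at ρ = 0.3 and 0.5. With a waning effect it also trails the interaction F at every ρ.

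This is an avoidable loss of precision and a diluted estimate, not an invalid test. It should be fixed.

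**What to change.** In Statistical analysis:

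1. Use months 3, 6 and 12 as the outcome visits, with the same marker's month 0 value as a fixed covariate whatever its baseline p-value. ANCOVA will do, or a repeated-measures mixed model with treatment, visit, treatment-by-visit, baseline and baseline-by-visit.
2. Name one baseline-adjusted contrast as the treatment comparison and report it with a 95% CI. The mean of months 3, 6 and 12 directly replaces the four-visit F and is more efficient for any effect shape under the assumptions above. Month 12 is the choice if the question is the effect at one year or if the effect is expected to build.
3. Do not use the unadjusted four-visit F or the unadjusted post-treatment comparison as the treatment test. The interaction F may stay as a supporting test.

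The cost is SAP wording and a little more analysis work, with the same data and software.

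### Twenty-three markers are each tested at p<0.05 with no primary outcome, visit or test and Bonferroni only for post hoc comparisons, so the familywise error is uncontrolled

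*Combined protocol and SAP*

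**What the plan says.** The title and Objectives single out three constructs. The purpose is to study changes in arterial stiffness and in "endothelial glycocalyx thickness and coronary reserve flow (CFR) after treatment with metformin or agonist GLP-1R". Under Design, "It will be a randomized study with metformin or GLP-1R agonist treatment for 1 year".

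Methods items a to c give four vascular indices: pulse wave velocity (PWV), augmentation index (AI), perfused boundary region (PBR) and CFR. Item d adds a blood panel ("Determination of the following parameters in blood: glucose, insulin, free fatty acids, triglycerides, glycerol, C reactive protein (CRP" and so on), which comes to 19 markers. All are measured at 0, 3, 6 and 12 months.

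The Statistical analysis section does not separate these sets. It plans t-tests or rank tests on every measured variable. It also plans a repeated-measures ANOVA with a time-by-treatment F test, and adds: "The F and P values of the comparison between treatments will be calculated". Further on: "Comparisons between baseline or post-treatment values of measured markers between the 2 treatment groups will be performed using factorial ANOVA".

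The only threshold is "Statistical significance will be considered as $p < 0.05". The only multiplicity adjustment, stated twice, is "Post hoc comparisons will be performed with Bonferroni correction".

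**The concern.** The plan names three constructs of interest but does not say which measure, visit and test would answer the question. Arterial stiffness alone has two measures, with neither preferred. Each marker has two treatment-related F tests plus comparisons of post-treatment values, and there are three post-baseline visits.

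The Bonferroni statements apply after an ANOVA and, at most, within one marker. They do not cover the F tests themselves or the number of markers.

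A significant result on any marker, by any of these tests, could therefore be presented as the trial's finding. A reader could not tell that it had been selected, and the nominal 5% would understate the chance that it is false. This cannot be repaired once results by arm are known.

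**Working it through.** The documents give no overall error rate, power or sample-size calculation, so there is no figure of the plan's own to reproduce.

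**Inputs from the documents**
- Per-test level 0.05 (Statistical analysis). Sidedness is not stated; two-sided is assumed.
- Vascular indices (Methods a to c): PWV, AI, PBR, CFR = 4.
- Blood markers (Methods d): glucose, insulin, free fatty acids, triglycerides, glycerol, CRP, TGF-b (7); Lp-PLA2, TNF-a, IL6, IL10, PIP, PIIINP (6); MMP-9, MMP-2, M-CSF, GDF-15, NT-proBNP, galectin-3 (6). Total 7 + 6 + 6 = 19.
- All markers: 4 + 19 = 23.

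**Assumptions not in the documents**
- No true difference on any marker, and one test per marker.
- A common correlation r between test statistics, shown over a range because none is given.

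**Familywise error with independence: 1 − 0.95^k**
- k = 3: 1 − 0.95^3 = 0.143
- k = 4: 1 − 0.95^4 = 0.185
- k = 21: 1 − 0.95^21 = 0.659
- k = 23: 1 − 0.95^23 = 0.693

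The k = 21 row leaves out glucose and insulin, because Objectives says of this drug class that "These drugs lower glucose levels by inhibiting the secretion of glucagon, promoting the release of insulin in response to hyperglycemia", so a null effect on those two is not credible.

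**With correlation.** For equicorrelated normal statistics, r = 0.3 and 0.5 come from numerical integration and r = 0.8 from simulation:

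| Family | k | r = 0 | r = 0.3 | r = 0.5 | r = 0.8 |
|---|---|---|---|---|---|
| Title outcomes, one measure each | 3 | 14.3% | 13.6% | 12.5% | 9.8% |
| Vascular indices | 4 | 18.5% | 17.4% | 15.6% | 11.4% |
| All except glucose and insulin | 21 | 65.9% | 55.5% | 42.9% | not computed |
| All markers | 23 | 69.3% | 58.2% | 44.9% | about 23% |

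**One direction only.** For a false difference favouring the GLP-1R agonist, the formula is 1 − 0.975^k: 7.3% (k = 3), 9.6% (k = 4), 41.2% (k = 21) and 44.1% (k = 23) with independence. At r = 0.5 these are 6.3%, 7.8%, 21.6% and 22.5%.

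**Two F tests per marker.** Simulation used 45 v 45 patients (an assumed equal split of the 90), four visits, between-visit correlation 0.3, 0.5 or 0.7, and 20,000 draws each. At least one of the two F tests had p<0.05 in 9.8%, 10.0% and 9.9% of draws. Across three independent outcomes this gives 26.7%, 27.1% and 26.7%. The analytic check, 1 − 0.95^6 = 0.265, agrees.

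**Effect of adjusting.** Bonferroni over three outcomes uses 0.05/3 = 0.0167 per test, and 1 − (1 − 0.0167)^3 = 0.049. An effect with 80% power at 0.05 has a standardised size of 1.960 + 0.842 = 2.802. At 0.0167 the critical value is 2.394, so power is Φ(2.802 − 2.394) = Φ(0.408) = 0.658.

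**The case against.** The strongest reply is that the title and purpose already confine the question to three constructs, so 69% describes a family the plan never puts forward as its question. That has force: for the study question the relevant range is about 13% to 19% (r from 0 to 0.5), and 69% is a ceiling that needs independence and 23 true nulls. But 13% to 19% is still well above 5%, and nothing in the analysis section gives the three constructs priority.

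Four narrower points:
- The 14% assumes one measure per construct. As written, stiffness has two, so the four-index figure of 19% describes the plan at least as well. This makes 14% the lower of the two.
- The directional figures apply to a signed contrast. The time-by-treatment F test has no direction, and the documents define no favourable direction for most blood markers. These figures are supplementary and the conclusion does not need them.
- The interaction F is one omnibus test over all visits, and post hoc comparisons are Bonferroni-corrected, so multiplicity across visits is partly handled. Multiplicity across markers and across alternative tests is not.
- The work might be meant as exploratory. The documents do not say so; they describe a one-year randomized comparison with a significance rule. If exploration is the intention, that also needs to be written down.

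**Conclusion.** The concern holds. The plan names no primary outcome, visit or test, and its only adjustment does not reach across markers or F tests.

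With no true differences and one two-sided test per marker, the chance of at least one false positive is 14% for the three title outcomes and 69% for all 23 markers under independence. No correlation examined restores 5%: even at r = 0.8 the figures are about 10% and 23%. Counting both planned F tests raises the three-outcome figure to about 27% if the outcomes are independent.

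The exact sizes depend on the assumed correlations. The absence of control does not. This must be fixed before analysis.

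**What to change.** Before any outcome data by arm are seen, amend the Statistical analysis section as follows.

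1. Name one between-arm comparison, GLP-1R agonist against metformin, as confirmatory; month 12, the end of the planned treatment year, is one option. Apply it to one measure of each title outcome, for example carotid-femoral PWV, PBR and CFR.
2. State whether the comparison pools the three populations of 30 and how baseline enters. One option is all 90 patients, with population and the outcome's baseline value as covariates.
3. Control the familywise error across the three outcomes at two-sided 0.05 with Holm, or with a fixed sequence if the sponsor justifies an order.
4. Report the stiffness measure not chosen and the 19 blood markers as secondary, with false discovery rate control.
5. Label the other visits, the remaining F tests and the correlations exploratory.

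A repeated-measures test could serve as the confirmatory comparison, provided it is the only one named.

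The cost is wording only, with no new data or visits. One named contrast replaces the two F tests as the basis for inference on the title outcomes. Fewer markers can be called significant, and at Holm's strictest step (0.0167) an outcome with 80% power at 0.05 has about 66%. The documents do not say whether data by arm have been seen; if they have, the amendment cannot be presented as prespecified.

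### Covariates are chosen partly by a p<0.05 baseline test between randomised arms, and nothing ensures that post-treatment comparisons adjust for the marker's own month-0 value

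*Combined protocol and SAP*

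**What the plan says.** Under Design, treatment is randomised: "It will be a randomized study with metformin or GLP-1R agonist treatment for 1 year". The same section recruits three populations of 30: T2DM without CAD, T2DM with CAD, and obesity with abnormal OGTT ("The investigators will study three groups matched for age and sex"). Under Methods, all markers are taken at four time points, including month 0: "At 0, 3, 6 and 12 months the investigators will measure".

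The Statistical analysis section plans two relevant between-arm analyses.

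- **Repeated-measures ANOVA.** Months 0, 3, 6 and 12 are levels of a within-subject factor, and the F and P "values of the interaction between time of measurement of the examined markers and type of treatment will be calculated".
- **Comparison of values (final paragraph).** "Comparisons between baseline or post-treatment values of measured markers between the 2 treatment groups will be performed using factorial ANOVA".

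The final paragraph then gives the covariate rule. The first part is "Baseline variables that will be statistically different ($p < 0.05$) among the 2 study groups or will be of clinical significance"; the variables of clinical significance are listed as "HbA1c, weight, BMI and waist circumference) will be included in multivariate models as covariates". The plan does not say which analyses count as multivariate models.

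For skewed markers: "Data with a non-gaussian distribution will be expressed as median (interquartile range) and will be analyzed after transformation into ranks".

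No section names a marker's own month-0 value as a covariate, and no analysis is named as primary.

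**The concern.** The 2 study groups in the covariate rule must be the randomised arms, since the same paragraph speaks of 2 treatment groups and the recruited populations number three. Between randomised arms, a significant baseline difference is a chance event. Testing for it says nothing about whether the variable predicts the outcome, and that is the property that makes a covariate useful.

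Two things follow for the between-arm comparison of post-treatment values.

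- The natural candidate covariate, the same marker at month 0, is not on the clinical list. It enters only if it happens to differ between arms at p<0.05, so the precision it offers is normally discarded.
- Part of the covariate set is unknown until the baseline data have been seen, and can differ from trial to trial by chance.

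There is also a conditional problem. If an imbalance just misses significance, the rule withholds adjustment where it is most needed.

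**Working it through.** The documents state no power, effect size, SD, allocation ratio or baseline-outcome correlation, so there is no planned figure to reproduce. What follows is illustration on assumed inputs.

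**Inputs from the documents.** Total 90 patients (3 × 30, Design); significance level 0.05 (Statistical analysis; taken as two-sided); 23 markers under Methods (PWV, AI, PBR, CFR and 19 blood measures).

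**Assumptions.** 1:1 allocation, so n = 45 per arm; effect d = 0.5 SD; one post-treatment visit; no dropout; correlation r between month-0 and post-treatment value of 0, 0.3, 0.5 or 0.7.

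**Step 1: how often the screen fires.** Under randomisation each baseline test is significant with probability 0.05, so own baseline enters in about 5% of trials (simulated 4.9% to 5.2%). Across all markers, 23 × 0.05 = 1.15 are expected to be flagged by chance.

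**Step 2: power by formula.** The noncentrality is d√(n/2) without adjustment and d√(n/2)/√(1−r²) with own baseline.

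- Unadjusted: 0.5 × √22.5 = 2.372, power 65.0%.
- r = 0.3: 2.372/√0.91 = 2.486, power 69.1%.
- r = 0.5: 2.372/√0.75 = 2.739, power 77.3%.
- r = 0.7: 2.372/√0.51 = 3.321, power 90.7%.

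The smallest effect with 80% power falls from 0.60 SD unadjusted to 0.57, 0.52 and 0.43 SD at r = 0.3, 0.5 and 0.7.

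**Step 3: power under the plan's rule.** Simulation with bivariate normal month-0 and post-treatment values in a linear model. Own baseline is entered only if its between-arm p<0.05 (screen) or always. There were 40,000 trials per setting (20,000 for ranks).

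| Setting | Method | r = 0 | r = 0.3 | r = 0.5 | r = 0.7 |
|---|---|---|---|---|---|
| 45 per arm | screen | 64.6% | 65.0% | 66.1% | 66.5% |
| 45 per arm | always | 64.1% | 68.3% | 77.1% | 90.4% |
| 36 per arm (20% dropout) | screen | – | 55.5% | 55.8% | 56.8% |
| 36 per arm (20% dropout) | always | – | 58.6% | 66.8% | 83.0% |
| 45 per arm, on ranks | screen | – | 63.2% | 63.8% | 65.4% |
| 45 per arm, on ranks | always | – | 66.3% | 73.7% | 87.4% |

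The screen recovers almost none of the available gain.

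**Step 4: with the four clinical covariates always in.** 20,000 trials. Weight, BMI and waist are correlated 0.7 with each other, HbA1c is independent of them, and each correlates c with both the month-0 and the post-treatment value. Entries are screen against always.

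| c | r = 0.3 | r = 0.5 | r = 0.7 |
|---|---|---|---|
| 0 | 63.0% / 66.1% | 63.5% / 74.6% | 64.2% / 89.0% |
| 0.2 | 67.0% / 69.1% | 67.7% / 76.6% | 68.6% / 89.5% |
| 0.4 | 81.4% / 81.3% | 81.9% / 83.4% | 82.4% / 91.8% |

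**Step 5: type I error.** Overall, at r = 0.3 / 0.5 / 0.7, it is 4.7% / 4.5% / 3.7% under the screen and 5.0% / 5.1% / 5.0% with own baseline always in. The screen is slightly conservative.

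Conditionally on a baseline imbalance of z = 1.9, which the screen leaves unadjusted, the post-treatment test statistic under the null has mean 1.9r and SD √(1−r²). At r = 0.5 the mean is 0.95 and the SD 0.866. The chance of exceeding ±1.96 is 12.2%. At r = 0.3 and 0.7 it is 7.7% and 18.9%.

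**The case against.** The strongest reply is that the stated purpose is change in the markers, and the time-by-treatment interaction already addresses that using month 0. Assume 0.5 SD at all three post-treatment visits, equal correlations and no dropout. The interaction then has noncentrality 22.5 × 0.1875/(1−r), where 0.1875 is the sum of squares of the profile (0, 0.5, 0.5, 0.5) about its mean. That is 6.03, 8.44 and 14.06 at r = 0.3, 0.5 and 0.7, giving power of about 51%, 67% and 89% on 3 and 264 degrees of freedom. So at r = 0.7 the plan already holds a test almost as strong as the adjusted comparison. This limits the harm but does not remove it. A gap remains at 0.3 and 0.5, and the final-paragraph comparison is planned in its own right with nothing ranking it below the interaction.

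Other points deserve weight.

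- The multivariate models may not include the factorial ANOVA. The screen figures then describe nothing planned, but that comparison has no baseline adjustment at all, so the defect remains on either reading.
- Strong clinical covariates absorb much of the gain (step 4, c = 0.4). The c = 0.4, r = 0.3 cell implies a slightly negative partial correlation and should not be relied on either way.
- If each population is analysed alone, with about 15 per arm, power is about 25–26% under the screen against 27% / 33% / 44%.
- The rank results come from normal data, whereas the plan uses ranks for non-Gaussian data.
- The rule is written in advance and uses only baseline data, so the unfixed model is a mild fault.
- Population may already be a factor in the factorial ANOVA, whose factors are not named. The simulation assumed no true population effect, so it shows that term's cost and not its benefit.

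**Conclusion.** The concern holds, as a matter of efficiency and prespecification and not of validity. It is confined to the between-arm comparison of post-treatment values and does not touch the time-by-treatment interaction.

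In the base case (45 per arm, 0.5 SD, no clinical covariates), the screen forgoes about 3, 11 and 24 percentage points of power at correlations of 0.3, 0.5 and 0.7. At zero correlation nothing is forgone. The size depends on correlations, an effect size and an allocation ratio that the documents do not give, and it falls when the clinical covariates are strongly related to the marker. The textual finding depends on none of these: the screen is explicit, and own baseline is assured by neither route. The change should be made.

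**What to change.** - Delete the p<0.05 baseline screen.
- In every between-arm comparison of post-treatment values under the final paragraph of Statistical analysis (months 3, 6 and 12, each visit separately), prespecify the marker's own month-0 value and the patient population (the three recruited groups) as covariates.
- Where a marker is analysed on ranks, rank both the month-0 and the post-treatment values and fit the same model.
- Keep HbA1c, weight, BMI and waist circumference only as a fixed list, and name the models to which the list applies.
- Leave the repeated-measures ANOVA and its time-by-treatment interaction as planned. Do not add the own month-0 value as a covariate there, where it is already a response.
- The section also plans t-tests and Mann-Whitney tests. If these are meant to compare post-treatment values between arms, say how they rank against the adjusted comparison.

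The cost is a small edit to the SAP, one degree of freedom for own baseline and two for population. In simulation the population terms cost at most 0.1 percentage points of power, and own baseline costs about 0.5 points if its correlation with the outcome is zero. No new patients, visits or measurements are needed, and no planned test is lost.
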